2. AIMS AND HYPOTHESES

This pilot study seeks to assess the impact of a three-day mindfulness intervention on the stress response of Singaporean adults aged 21 or more. Specifically, we will anticipate a modest yet discernible reduction in stress levels compared to a control condition, represented by a sham meditation group.

In addition to evaluating the effectiveness of the decentralized mindfulness intervention and its comparison with the sham meditation control group, this study will also incorporate an assessment of the credibility and usability of the survey-based methodology employed.

Participants' feedback regarding the clarity of survey instructions, ease of navigation, and overall user experience will be solicited through post-intervention questionnaires. Insights gleaned from participants' perspectives will inform refinements to the methodology, ultimately optimizing its utility for a fully decentralized study on mindfulness on a larger scale.

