5.3.2 Pre and post measurements

The Five Facet Mindfulness Questionnaire – Short Form (FFMQ-SF; Bohlmeijer et al. 2011). The scale is recommended for comparing pre and post interventions that employ mindfulness training. The scale measures 5 different components; *Observing*; the ability to notice and pay attention to the thoughts, feelings, and surroundings. *Describing*; the attitude to express the experiences in words, to describe thoughts and emotions. *Acting with Awareness*; How well they can act with intention and full awareness in their daily activities, rather than on autopilot. *Non-judging of Inner Experience*; tendency to avoid judging their thoughts and emotions as good or bad. *Non-reactivity to Inner Experience*; tendency to experience thoughts and emotions without reacting impulsively. However, recent hierarchical confirmatory factor analysis indicates a preference for a four-factor FFMQ (excluding the 'observe' subscale) in non-meditative samples, as opposed to the traditional five-factor score (Gu et al., 2016). Consequently, the analysis will focus on four facets: Describing,

acting with awareness, non-judging, and non-reactivity. Examples of items are "I can describe my feelings well" or "I can easily talk about my thoughts and opinions" (answered on a five-point scale ranging from 1 = never or very rarely to 5 = Very often or always true). We will take this assessment at baseline and at the end of the experiment.

Repeated measurements (day 1, day 2, day 3)

State Trait Anxiety Inventory (STAI-6; Marteau TM, Bekker) The STAI-6 is a validated short-form version of the 40-item State-Trait Anxiety Inventory (STAI), consisting of 6 items that measure current anxiety symptoms using a 4-point Likert scale. Example items include statements such as "I feel calm" and "I am tense." The STAI-6 will be administered twice daily: once before and once after listening to each audio track.

Ecological Momentary Assessment – (EMA) Participants will indicate their current state on a 7-point Likert scale, with the options "Very Bad," "Bad," "Fairly Bad," "Same as Before," "Fairly Good," "Good," and "Very Good," encoded as [1, 2, 3, 4, 5, 6, 7], respectively. The following questions will be posed to assess various psychological and physical states:

- "Right now, I feel mentally sharp" – to assess perceived cognitive ability.
- "Right now, I feel fatigued" – to assess fatigue and exhaustion.
- "Right now, I feel stressed" – to assess stress levels.

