The Qualtrics link contains the written informed consent form and the actual experiment. Participants will be able to review all relevant information about the study and either accept or decline to participate. If they do not provide consent, they will be opted out of the study. If consent is provided, participants will proceed to the second screening, which involves answering additional questions about their use of concomitant medication. If they meet the criteria for this stage, they will proceed to answer questions about any neurological or psychiatric conditions. If any of the screening criteria are not satisfied at any point, the study will automatically terminate. Once consent and second screening are complete, participants will then be instructed to move to a quiet environment where they will not be disturbed for the next 35 minutes. They will be asked to download the 'Camera Heart Rate Variability' app and take an initial HRV measurement for testing purposes. Participants will then submit the generated CSV file to the study coordinator via WhatsApp and self-report their rMSSD values in the Qualtrics survey. Participants are instructed to label their CSV files using their anonymous identifier provided by the study coordinator via WhatsApp at the start. Afterward, they will complete a series of questionnaires, including the 20-item IPIP scale, the RS-14, the FFMQ, and various demographic questions such as age, gender, ethnicity, smartphone type used during the experiment, and its operating system (iOS or Android) and version. Pre-intervention assessments of STAI-6, EMA will also be conducted. They will then use the 'Camera Heart Rate Variability' app to measure HRV, submit the generated CSV file to the study coordinator, and self-report their rMSSD values in the Qualtrics survey, as outlined in the instructions.

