Participants will then be randomly assigned by the Qualtrics engine to either the experimental group, which listens to a mindfulness audio track, or the control group, which listens to a 'sham meditation' track. Both tracks are embedded within the Qualtrics survey. Participants cannot skip this portion of the survey for 10 minutes, ensuring they listen to the entire 10-minute audio track. Afterward, participants will be asked to sit quietly for three minutes without engaging in any activities. This pause is necessary because, some of the audio track encompasses the application of mindfulness principles while performing a routine activity (e.g., brushing teeth) during the listening of a mindfulness track. Although the movement involved in this activity is minimal, we want participants to sit still for three minutes to avoid introducing any confounding variables in the subsequent HRV assessments. The survey will be programmed to remain stuck during this period to prevent participants from skipping this step.

Following the quiet period, participants will complete post-intervention assessments for STAI-6, EMA and HRV. Participants will be thanked and instructed to reopen the survey link the following day, ideally at the same time between 9am and 9pm. On Day 2, they will complete the same pre-intervention assessments (STAI-6, EMA and HRV), listen to a different audio track, either mindfulness or sham meditation, depending on their group allocation, sit for three minutes, and then complete the post-intervention assessments mirroring Day 1. On Day 3, participants will undergo the same procedure as Day 2 but will listen to another audio track (mindfulness or sham). Additionally, they will complete the FFMQ, answer questions about their expectations of the intervention, its credibility, the PARH scale, and the usability questionnaire. Finally, participants will be thanked for their participation in the study and debriefed.

6. Ethics information

This study will be conducted in accordance with the ethical principles outlined in the Declaration of Helsinki and in compliance with applicable regulatory requirements. The final study protocol, along with the latest version of the Participant Information and Consent Form, will receive written approval from the A*STAR Institutional Review Board (A*STAR IRB) before any participants are enrolled.

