8. SAMPLE SIZE AND STATISTICAL METHODS

8.1. Determination of Sample Size.

Since this is a pilot trial, we aim to recruit 60 participants to account for a ~20% dropout rate, ensuring we meet our target of at least 50 participants.

8.2. Statistical analyses.

Our confirmatory statistical analyses will include:

- Bayesian mixed-effects models to investigate the longitudinal changes in self-reported stress measured via STAI-6. The model will have STAI-6 as the

dependent variable, with 'Group' (mindfulness intervention or control), 'Day' (1 to 3), and their interaction term as independent variables. Participant ID will be used as a random intercept to control for individual differences. A BF10 greater than 1 will indicate slightly positive evidence supporting the effectiveness of the mindfulness condition over the control condition in stress reduction.

We will also conduct the following exploratory statistical analyses:

- A Bayesian mixed-effects model to assess longitudinal changes in HRV, using HRV as the dependent variable and 'Group', 'Day' (1 to 3), and their interaction as independent variables. Participant ID will again serve as a random intercept. A BF10 greater than 1 will suggest positive evidence for the mindfulness intervention's effectiveness compared to the control.
- An additional Bayesian mixed-effects model will analyze longitudinal changes in HRV, with the dependent variable being HRV (calculated by the difference in pre- and post-meditation HRV scores) and independent variables including 'Group', 'Day' (1 to 3), and their interaction. Participant ID will account for individual variability in baseline HRV levels.
- Correlational analyses to explore the relationship between changes in mindfulness scores and stress levels, as well as between HRV changes and stress levels.
- Descriptive statistics to summarize baseline participant characteristics, such as neuroticism, RS-14 scores, FFMQ scores related to mindfulness training, and demographic details.
- Analysis of responses regarding the intervention's credibility and participant awareness of the research hypothesis to assess equal credibility of the intervention for the mindfulness condition and the sham.

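### The confirmatory STAI-6 Bayes factor has no defined score, term, comparator model or prior, and its only cut-off (BF10 > 1) leaves no inconclusive zone

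*Combined protocol and SAP*

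**What the plan says.** Section 8.2 names one confirmatory analysis: a Bayesian mixed model for STAI-6 with Group, Day (1 to 3) "and their interaction term as independent variables", plus a participant random intercept. The only reading rule is "A BF10 greater than 1 will indicate slightly positive evidence supporting the effectiveness of the mindfulness condition over the control condition in stress reduction". The first exploratory HRV model uses the same cut-off with a stronger label: "A BF10 greater than 1 will suggest positive evidence".

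On timing, section 5.3.2 states: "The STAI-6 will be administered twice daily: once before and once after listening to each audio track". That makes 2 × 3 = 6 scores per participant. In section 5.4 the Day 1 sequence is "Pre-intervention assessments of STAI-6, EMA will also be conducted", then an HRV reading, and only then "Participants will then be randomly assigned by the Qualtrics engine to either the experimental group".

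The second HRV model does define its outcome, as HRV "calculated by the difference in pre- and post-meditation HRV scores". The STAI-6 model has no such definition. Section 2 gives the expected direction in words: "we will anticipate a modest yet discernible reduction in stress levels compared to a control condition".

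**The concern.** A Bayes factor compares two models fitted to a defined outcome. Here neither model is identified. BF10 could refer to the Group main effect, to Group by Day, or to both together. The stated interest in change over time points to the interaction, while the rule's wording about one condition against the other points to Group. No prior is given, although the prior moves the cut-off. Nothing says whether pre-track, post-track, all or change scores are analysed. Taken at face value, the model pools all six scores, and one of these precedes allocation.

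The cut-off adds to this. BF10 = 1 is the neutral point, yet every value above it is to be read as favourable, and no range is set aside as inconclusive. The confirmatory result could therefore turn on choices made after the data are seen, and a nearly uninformative value could be reported as support.

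**Working it through.** **Inputs from the plan.** 60 recruited, about 20% dropout, at least 50 wanted (section 8.1; 50 × 1.20 = 60). Two arms, six STAI-6 scores each. The plan states no error rate or power for the BF10 rule, so there is no operating figure to reproduce.

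**Assumed, not in the documents.** 1:1 allocation, so 25 per arm; a two-sample t approximation with 48 df; a Cauchy prior on the standardised difference d with scale r = 0.2, 0.707 or 1.0; equal correlation ρ = 0.5 between scores; a benefit of 0.3 single-score SD on each post-track score.

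**1. What values near 1 mean.** At equal prior odds the probability of an effect is BF/(1 + BF). BF10 = 1.1 gives 1.1/2.1 = 52%; BF10 = 3 gives 75%.

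**2. The cut-off with no effect.** BF10(t) is the noncentral t density (48 df, noncentrality d√(25/2) = 3.54d), averaged over the Cauchy prior, divided by the central t density at t.

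| | r = 0.2 | r = 0.707 | r = 1.0 |
|---|---|---|---|
| \|t\| at which BF10 = 1 | 1.47 | 1.77 | 1.89 |
| BF10 > 1, either direction | 14.7% | 8.3% | 6.5% |
| of which favouring mindfulness (half) | 7.4% | 4.2% | 3.2% |
| share of crossings with BF10 only 1 to 3 | 90% | 78% | 75% |

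The unstated prior alone changes the verdict for any |t| between 1.47 and 1.89.

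**3. Which scores enter.** Variances in single-score units at ρ = 0.5:
- Six-score mean: (1 + 5ρ)/6 = 0.583. With no carry-over into the Day 2 and Day 3 pre-track scores, the mean benefit is 0.3 × 3/6 = 0.15, so d = 0.15/√0.583 = 0.20. With full carry-over it is 0.3 × 5/6 = 0.25, so d = 0.33.
- Post-track mean: (1 + 2ρ)/3 = 0.667, so d = 0.3/√0.667 = 0.37.
- Post-track mean adjusted for the Day 1 pre-track score: 0.667 − ρ² = 0.417, so d = 0.3/√0.417 = 0.46.

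| BF10 > 1 | r = 0.2 | r = 0.707 | r = 1.0 |
|---|---|---|---|
| Six scores, no carry-over | 24% | 16% | 13% |
| Six scores, full carry-over | 39% | 28% | 24% |
| Post-track only | 44% | 33% | 29% |
| Post-track, adjusted | 57% | 46% | 41% |

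At r = 0.707, correlations of 0.3 to 0.7 give 14–18% (six scores, no carry-over), 29–38% (post-track) and 44–56% (adjusted). On the same simulated data the six-score and post-track verdicts differ in 23/19/17% of trials without carry-over and in about 13/11/10% with full carry-over. The no-effect rates are the same for all the scores.

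**4. Which term.** A benefit that is constant over days contributes nothing to Group by Day. A linear interaction contrast therefore crosses 1 only at the no-effect rates, 14.7/8.3/6.5%. The plan does not say how Day is coded, and a three-level Day gives a 2-df interaction. A BIC approximation for that case (one score per day, within-person correlation 0.5, penalty N = 50, constant 0.2 SD benefit) gives BF10 > 1 in 14.3% for Group, 2.2% for the interaction and 2.5% for both together.

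**The case against.** BF10 above 1 does favour the alternative by definition, and the confirmatory wording is hedged. The study is a pilot with no success criterion or go/no-go rule, nothing prevents the team from reporting the value itself, and limits of 3 and 1/3 are only conventions. All of that stands. The cut-off wording alone would be a minor point. The heavier fault is that BF10 is undefined in an analysis the plan itself calls confirmatory. Relabelling that analysis as estimation would ease the threshold problem but would still leave the score undefined.

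Three stronger readings are tempting, and the documents do not support them.
- *Pooling a pre-randomisation score biases the result toward mindfulness.* It does not. That score cannot differ systematically by arm, so it dilutes the contrast, and the no-effect rates are unchanged.
- *Direction is missing, so a sham-better result would be declared a mindfulness success.* Section 2 and the rule itself give the direction in words. What is missing is only the link to the sign of the estimate. With a true benefit of 0.3 SD of the analysed score, a sham-better BF10 > 1 occurs in 0.6/0.3/0.2% of trials.
- *Pooling six scores must cost a great deal.* That depends on carry-over, which the documents do not address. With full carry-over the gap to post-track scoring is about 5 points.

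The 90/78/75% share of weak crossings also applies only when there is no effect. At d = 0.46 it is about 66/51/49%.

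**Conclusion.** The point holds and should be fixed before data are seen. That the score, term, comparator and prior are unstated follows from the text and needs no assumption. The literal six-score reading follows from setting sections 5.3.2, 5.4 and 8.2 side by side; the plan does not say that the team intends it. Under the stated assumptions, moving from that reading to adjusted post-track scores raises the chance of BF10 > 1 for a real benefit from 24/16/13% (no carry-over) or 39/28/24% (full carry-over) to 57/46/41%. False support for mindfulness is about 7.4/4.2/3.2% if the sign is respected. These figures illustrate how far the open choices matter. They are not the trial's own operating characteristics, because the plan fixes too little to compute those. What is at stake is how the confirmatory result is interpreted; the plan attaches no decision to it.

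**What to change.** Amend section 8.2 as follows.
1. Outcome: the three post-track STAI-6 scores, with the Day 1 pre-track score as covariate, Day as a factor and a participant random intercept. Report Day 2 and Day 3 pre-track scores separately.
2. Confirmatory BF10: this model with versus without the Group main effect (the Group difference averaged over days, as a model contrast), with Day in both models. Report Group by Day as secondary.
3. Fix one prior scale in advance and show others as sensitivity analyses.
4. Read BF10 as support only if the estimate favours mindfulness.
5. Replace the cut-off of 1 with wording that includes an inconclusive zone, for example 1/3 to 3 (a convention, not from the documents). Do the same for HRV in its own favourable direction.
6. Lead with the posterior mean difference and its 95% credible interval.

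**Cost.** Wording only; no new data. The Day 2 and Day 3 pre-track scores leave the confirmatory contrast.

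Most pilots of this size would be called inconclusive. With a true benefit of 0.3 SD of the analysed score and a directional Bayes factor, 17/17/15% exceed 3, 83/63/55% are inconclusive and 0.4/20/30% fall below 1/3. At the two wider scales a real benefit therefore falls below 1/3 more often than above 3 (20% v 17%, 30% v 15%).

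An undirected BF10 with the sign condition is harsher. About 8/9/8% exceed 3 in the right direction. Values below 1/3 need |t| under 0.63 at scale 0.707 or 1.01 at scale 1.0, and cannot occur at 0.2. With noncentrality 0.3 × 3.54 = 1.06, that is about 0/29/46%. The interval, not the band, should carry the conclusion.

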- "Right now, I feel nervous" – to assess nervousness and tension.
- "Right now, I feel depressed" – to assess depressive symptoms.
- "Right now, I am in a good mood" – to assess positive affect and joy.
- "I slept well last night" – to assess subjective sleep quality.

Ecological Momentary Assessment (EMA) will be conducted twice daily, immediately following each administration of the STAI-6 questionnaires.

Heart Rate Variability. To assess parasympathetic activation, participants' heart rate variability (HRV) will be analyzed. HRV is widely recognized as a sensitive marker of stress, regulated by the autonomic nervous system in response to stressors (Goldberger et al., 2001). Participants will monitor their HRV using the 'Camera Heart Rate Variability' smartphone app, which employs Photoplethysmogram (PPG) technology. Notably, smartphone apps utilizing PPG for heart rate measurement have shown consistency with validated methods such as electrocardiography (ECG) in adult populations during resting states (Gudeo-Fernández et al., 2020).

Participants will assess their HRV values seven times over the course of the trial (from Day 1 to Day 3). Participants will be instructed to place their index finger over the smartphone's camera and flash, ensuring both are fully covered. They will hold their finger in place for one minute to allow the device to record their heart rate variability (HRV). Upon completion, the HRV measurement will be saved in the app's local folder. If the finger placement is inadequate, resulting in poor assessment quality, the app will indicate that the CSV file has not been created. In such cases, participants will be asked to repeat the assessment up to two more times. If they are still unable to obtain a valid measurement after the third attempt, they will be instructed to proceed to the next section of the survey.

Participants will then send the corresponding CSV file via email to the study coordinator using a feature included in the app, following the instructions provided at the beginning of the experiment. To ensure that HRV data is not lost, participants will also self-report the corresponding values in the Qualtrics survey.

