The first HRV measurement will serve as testing purposes and will be taken immediately after the survey that will prompt participants to go to a quiet place just after the start of the experiment. The additional HRV measurements will be taken twice daily, immediately following the completion of each Ecological Momentary Assessment (EMA).

One-time measurement (end of the trial)

Usability of the intervention to assess the usability of the current pilot trial, a set of questions will be asked to assess the participants' experiences with the mindfulness and sham meditation tracks in terms of ease of use, clarity of instructions, relevance to daily life, engagement levels, comfort, perceived efficacy, willingness to continue usage, any technical issues encountered, and suggestions for improvement.

Perceived Awareness of the Research Hypothesis (PARH; Rubin 2016) is a four-item quantitative self-report tool designed to assess the possible impact of demand characteristics in research settings. Its purpose is to assist in challenging the notion that observed effects can be attributed to demand characteristics. Participants provide their responses to these statements using a 7-point Likert-type scale, where the options range from strongly disagree (1) to strongly agree (7). Examples of statements include: "I was aware of the researchers' objectives in this study" and "I was uncertain about the researchers' intentions in conducting this research".

Expectancy and credibility of the intervention

To assess expectancy, we will use a single item adapted from the Credibility/Expectancy Questionnaire (Devilly & Borkovec, 2000) during the final phase of post-intervention testing: "On a scale from 0 to 10, How effective do you believe the meditation training has been in alleviating stress? (0 = Not at all successful, 10 = Extremely successful)."

To evaluate credibility, participants will respond to a two-part question: "If you were informed that you might have received either meditation training or control training, which type do you believe you received? (Meditation, Control)". "How confident are you in your answer? (0 = Not at all confident, 10 = Extremely confident)".

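### The exploratory HRV change model drops every session with one failed reading; a joint model of all six readings would use the valid one, for a small gain in precision

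*Combined protocol and SAP*

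**What the plan says.** **Readings.** Section 5.3.2 states: "Participants will assess their HRV values seven times over the course of the trial". One of these is not for analysis: "The first HRV measurement will serve as testing purposes". For the rest, "The additional HRV measurements will be taken twice daily". Each participant therefore has six analysed readings, in three pre/post pairs.

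**Failures.** The same section allows two repeats after a poor recording. It then says: "If they are still unable to obtain a valid measurement after the third attempt, they will be instructed to proceed to the next section". The reading stays missing and the session continues.

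**Models.** Section 8.2 introduces both HRV models with "We will also conduct the following exploratory statistical analyses". The first is "A Bayesian mixed-effects model to assess longitudinal changes in HRV, using HRV as the dependent variable", with Group, Day and Group by Day. The second has as its outcome a session change, "calculated by the difference in pre- and post-meditation HRV scores", with "independent variables including 'Group', 'Day' (1 to 3), and their interaction" and a participant effect.

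**Missing readings.** No section says what happens to a session with only one valid reading. There is no imputation rule and no reading-level model with a pre/post term. The value that participants also type into the survey protects against a lost file. It does not help when the app produced no reading.

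**The concern.** The change model is the only planned Group comparison of the acute HRV response to a track. A difference needs two numbers. If one reading fails, the session leaves the model and takes a valid reading with it.

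The protocol itself provides for such failures, and recordings are unsupervised, at home, on participants' own phones. A mixed model of the individual readings could use the lone reading, because readings from the same person and the same day are correlated. The first HRV model is reading-level, but without a pre/post term it does not estimate the acute effect.

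At stake is some precision on an exploratory estimate in a small pilot, and the risk that the same specification is carried into the planned multi-site study.

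**Working it through.** **1. Reading count.** 1 test + 2 per day × 3 days = 7, as section 5.3.2 states. With the section 8.1 target of 50 participants there are 50 × 3 = 150 sessions and 300 analysed readings.

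**2. Incomplete sessions.** Let f be the final failure probability of a reading, after all three attempts. The documents give no value, so f is assumed, with failures independent.

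- At least one reading failed: 1 − (1 − f)²
- Exactly one failed, so a valid reading is dropped: 2f(1 − f)
- Both failed, so nothing valid is dropped: f²

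| f | Failed readings (of 300) | Incomplete sessions (of 150) | Exactly one valid | Both failed |
|---|---|---|---|---|
| 5% | 15 | 14.6 (9.8%) | 14.2 | 0.4 |
| 10% | 30 | 28.5 (19%) | 27.0 | 1.5 |
| 20% | 60 | 54.0 (36%) | 48.0 | 6.0 |

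**3. Precision of the acute Group effect.** Generalised least squares information was averaged over all 64 patterns of valid and failed readings. Two models were compared: differences from complete pairs with a participant effect on change, and all valid readings with Day, pre/post and the same participant effect on change. Assumed SDs on the log scale, none of them from the documents: participant 0.5, day within participant 0.1 or 0.2, single reading 0.2, individual response (a participant-specific pre/post change) 0 to 0.2. The ratio is the variance with differences divided by the variance with all readings.

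| Response SD | Day SD | f = 0 | 5% | 10% | 20% |
|---|---|---|---|---|---|
| 0 | 0.1 | 1.00 | 1.032 | 1.068 | 1.148 |
| 0 | 0.2 | 1.00 | 1.020 | 1.041 | 1.090 |
| 0.1 | 0.1 | 1.00 | 1.028 | 1.060 | 1.134 |
| 0.1 | 0.2 | 1.00 | 1.017 | 1.037 | 1.084 |
| 0.2 | 0.1 | 1.00 | 1.020 | 1.044 | 1.107 |
| 0.2 | 0.2 | 1.00 | 1.013 | 1.028 | 1.071 |

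The loss is therefore 1-3%, 3-7% and 7-15% of variance. At 20% failure the standard error is √1.071 to √1.148, that is 1.03 to 1.07 times as large.

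Dropping the Group term at the Day 1 pre-track reading, which precedes randomisation, would save about a further 2% of variance even with no failures. That gain has nothing to do with failed readings and is left out of the table.

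**4. Why the replacement needs a random slope.** Participant and participant-by-day intercepts both cancel from a pre/post contrast. With those alone, three changes from one person are treated as independent. The true variance of the effect is 1 + 2ρ times the assumed one, where ρ = response variance / (response variance + 2 × reading variance).

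- Response SD 0.1: ρ = 0.01 / (0.01 + 0.08) = 0.111, factor 1.22
- Response SD 0.2: ρ = 0.04 / (0.04 + 0.08) = 0.333, factor 1.67

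A nominal 5% test then rejects about 8% or 13% of the time when there is no effect. A simulation with 25 per arm and complete data agrees (7.7% and 13.0%), and keeping the participant effect on change holds it at 5%. The planned change model already has that effect, so a replacement must not lose it.

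**The case against.** **The failure rates may be too high.** This has weight. With three independent attempts per reading, final failure of 5%, 10% or 20% needs 37%, 46% or 58% failure per attempt (the cube root of f). The test reading also gives practice. At a low rate the loss is negligible.

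**Failures may cluster.** If failure follows the phone or the user, both readings of a session tend to fail together. In the extreme no valid partner is lost and the ratio returns to 1.00.

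**The lone reading is not wasted.** This is true of the study as a whole, since the first HRV model can use it. It is not true of the acute effect, which that model does not estimate.

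**Readings that go too far.** Three inferences are tempting and unsupported.

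- A reader might infer that more sessions are lost than readings fail. The percentage roughly doubles because there are half as many sessions as readings. In number, slightly fewer sessions are lost than readings fail (28.5 against 30 at 10%).
- A reader might infer that only people whose phone always worked are kept. The model drops sessions, not people. At 10% failure about 27 of 50 participants have all three pairs (50 × 0.81³), but only 0.34 have none (50 × 0.19³).
- A reader might infer a biased result. Failures could depend on phone, movement or arm, but the documents give no information on this. A joint model would not cure failures that depend on the unseen value either.

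**Conclusion.** The point holds as a minor matter of efficiency. The change model cannot use a valid reading whose partner failed, the protocol foresees such sessions, and the plan has no rule for them. The cost is about 1-3%, 3-7% or 7-15% more variance on the acute Group effect at assumed independent failure rates of 5%, 10% or 20%.

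These figures rest on assumed failure rates and variance components. With a wider range of variance shares (participant 0.4-0.7, session 0-0.4 of the variance of a reading, no individual response variation) the ranges are 1-4%, 3-9% and 7-20%. Clustering of failures lowers them.

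The documents do not support reading this as a threat to the trial's main conclusion. Both HRV models are labelled exploratory, and the confirmatory STAI-6 analysis does not use these readings.

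**What to change.** Replace the HRV difference model in section 8.2 with one Bayesian mixed model on the six analysed readings:

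- fixed effects for pre/post, Day, Group and their interactions, with no Group term at the Day 1 pre-track reading, because section 5.4 places randomisation after it;
- participant and participant-by-day random intercepts;
- a participant-by-pre/post random slope, so that the three changes from one person are not treated as independent;
- Group by pre/post reported as the acute effect, with the number of valid readings by arm, day and time point.

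Sessions with one valid reading then contribute. The data, software and procedures stay the same. The cost is SAP wording and a slightly more complex model, with one more variance component to estimate and give a prior.
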